10.0 Adverse Event (AE) Reporting and Monitoring

10.1 Adverse Event Characteristics

CTCAE term (AE description) and grade: The descriptions and grading scales found in the revised NCI Common Terminology Criteria for Adverse Events (CTCAE) version 4.0 will be utilized for AE reporting. All appropriate treatment areas should have access to a copy of the CTCAE version 4.0. A copy of the CTCAE version 4.0 can be downloaded from the CTEP

web:(http://ctep.cancer.gov/protocolDevelopment/electronic_applications/ctc.htm)

10.11 Adverse event monitoring and reporting is a routine part of every clinical trial. First, identify and grade the severity of the event using the CTCAE version 4.0. Next, determine whether the event is expected or unexpected (see Section 10.2) and if the adverse event is related to the medical treatment or procedure (see Section 10.5). With this information, determine whether the event must be reported as an expedited report (see Section 10.4). Expedited reports are to be completed within the timeframes and via the mechanisms specified in Sections 10.4. All AEs reported via expedited mechanisms must also be reported via the routine data reporting mechanisms defined by the protocol (see Sections 10.6 and 18.0).

10.12 Each CTCAE term in the current version is a unique representation of a specific event used for medical documentation and scientific analysis and is a single MedDRA Lowest Level Term (LLT). Grade is an essential element of the Guidelines and, in general, relates to **severity** for the purposes of regulatory reporting to NCI.

NOTE: A severe AE, as defined by the above grading scale, is **NOT** the same as serious AE which is defined in the table in Section 10.4.

10.2 Expected vs. Unexpected Events

- The determination of whether an AE is expected is based on agent-specific information provided in Section 15.0 of the protocol and the study specific consent form.
- Unexpected AEs are those not listed in the agent-specific information provided in Section 15.0 of the protocol and the study specific consent form.

NOTE: “Unexpected adverse experiences” means any adverse experience that is neither identified in nature, severity, or frequency of risk in the information provided for IRB review nor mentioned in the consent form.

10.3 Assessment of Attribution

When assessing whether an adverse event is related to a medical treatment or procedure, the following attribution categories are utilized:

Definite - The adverse event *is clearly related* to the agent(s).

Probable - The adverse event *is likely related* to the agent(s).

Possible - The adverse event *may be related* to the agent(s).

Unlikely - The adverse event *is doubtfully related* to the agent(s).

Unrelated - The adverse event *is clearly NOT related* to the agent(s).

Events determined to be possibly, probably or definitely attributed to a medical treatment suggest there is evidence to indicate a causal relationship between the drug and the adverse event.

10.31 **AEs Experienced Utilizing Investigational Agents and Commercial Agent(s) on the SAME Arm**

NOTE: When a commercial agent(s) is (are) used on the same treatment arm as the investigational agent/intervention (also, investigational drug, biologic, cellular product, or other investigational therapy under an IND), the entire combination (arm) is then considered an investigational intervention for reporting-

Routine Reporting

- Routine AE reporting for Phase 1 and Phase 2 clinical studies using an investigational agent /intervention in combination with a commercial agent is stated in the protocol. See Section 10.6.
- Routine AE reporting for Phase 3 clinical studies using an investigational agent/intervention and a commercial agent in combination must be reported as defined by the general guidelines provided by sponsors, Groups, Cancer Centers, or Principal Investigators. See Section 10.6.

Expedited Reporting

- An AE that occurs on a combination study must be assessed in accordance with the guidelines for investigational agents/interventions in Section 10.4, and where indicated, an expedited report must be submitted.
- An AE that occurs prior to administration of the investigational agent/intervention must be assessed as specified in the protocol. In general, only Grade 4 and 5 AEs that are unexpected with at least possible attribution to the commercial agent require an expedited report. Refer to Section 10.4 for specific AE reporting requirements or exceptions.
- Commercial agent expedited reports must be submitted to the FDA via MedWatch.
- An investigational agent/intervention might exacerbate the expected AEs associated with a commercial agent. Therefore, if an expected AE (for the commercial agent) occurs with a higher degree of severity, expedited reporting is required. The clinical investigator must determine severity.

10.4 Expedited Reporting Requirements for IND/IDE Agents

10.41 Expedited Reporting Requirements for Adverse Events that Occur on Studies under an IND/IDE within 30 Days of the Last Administration of the Investigational Agent/Intervention^{1,2}

FDA REPORTING REQUIREMENTS FOR SERIOUS ADVERSE EVENTS (21 CFR Part 312) NOTE: Investigators MUST immediately report to the sponsor ANY Serious Adverse Events, whether or not they are considered related to the investigational agent(s)/intervention (21 CFR 312.64) An adverse event is considered serious if it results in ANY of the following outcomes:
 
 1) Death 2) A life-threatening adverse event 3) An adverse event that results in inpatient hospitalization or prolongation of existing hospitalization for \geq 24 hours 4) A persistent or significant incapacity or substantial disruption of the ability to conduct normal life functions 5) A congenital anomaly/birth defect 6) Important Medical Events (IME) that may not result in death, be life threatening, or require hospitalization may be considered serious when, based upon medical judgment, they may jeopardize the patient or subject and may require medical or surgical intervention to prevent one of the outcomes listed in this definition. (FDA, 21 CFR 312.32; ICH E2A and ICH E6 				

ALL SERIOUS adverse events that meet the above criteria MUST be immediately reported within the timeframes detailed in the table below.
				
Hospitalization	Grade 1 Timeframes	Grade 2 Timeframes	Grade 3 Timeframes	Grade 4 & 5 Timeframes
Resulting in Hospitalization \geq 4 hrs	7 Calendar Days			24-Hour 3 Calendar Days
Not resulting in Hospitalization \geq 24 hrs	Not required		7 Calendar Days	

NOTE: Protocol specific exceptions to expedited reporting of serious adverse events are found in section 10.6 of the protocol. Expedited AE reporting timelines are defined as:
 
 o “24-Hour; 3 Calendar Days” - The AE must initially be reported within 24 hours of learning of the AE, followed by a complete expedited report within 3 calendar days of the initial 24-hour report. o “7 Calendar Days” - A complete expedited report on the AE must be submitted within 7 calendar days of learning of the AE. 				

¹Serious adverse events that occur more than 30 days after the last administration of investigational agent/intervention and have an attribution of possible, probable, or definite require reporting as follows: Expedited 24-hour notification followed by complete report within 3 calendar days for:
 
 • All Grade 4, and Grade 5 AEs 
Expedited 7 calendar day reports for:
 
 • Grade 2 adverse events resulting in hospitalization or prolongation of hospitalization • Grade 3 adverse events 				

² For studies using PET or SPECT IND agents, the AE reporting period is limited to 10 radioactive half-lives, rounded UP to the nearest whole day, after the agent/intervention was last administered. Footnote “1” above applies after this reporting period.
				

Effective Date: May 5, 2011
				

10.42 Additional instructions:

Mayo Clinic Cancer Center (MCCC) Institutions: Attach copies of MedWatch 3500A to Mayo Clinic Cancer Center SAE Reporting Form: <http://livecycle2.mayo.edu/workspace/?startEndpoint=MC4158-56/Processes/MC4158-56-Process.MC4158-56> which will automatically be emailed to the MCCC Regulatory Affairs Unit (RAU) Risk Information Specialist at [contact], who will determine and complete IRB reporting. The RAU will submit to the MCCC SAE Coordinator and the MCCC IND Coordinator.

10.5 Adverse event reporting requirements for Merck

All adverse events will be recorded from the time the consent form is signed through 30 days following cessation of treatment and at each examination on the Adverse Event case report forms/worksheets.

10.51 Definition of an Overdose for This Protocol and Reporting of Overdose to the Sponsor and to Merck

For purposes of this trial, an overdose of pembrolizumab will be defined as any dose of 1,000 mg or greater (≥ 5 times the indicated dose). No specific information is available on the treatment of overdose of pembrolizumab. Appropriate supportive treatment should be provided if clinically indicated. In the event of overdose, the subject should be observed closely for signs of toxicity. Appropriate supportive treatment should be provided if clinically indicated.

If an adverse event(s) is associated with (“results from”) the overdose of a Merck product, the adverse event(s) is reported as a serious adverse event, even if no other seriousness criteria are met.

If a dose of Merck’s product meeting the protocol definition of overdose is taken without any associated clinical symptoms or abnormal laboratory results, the overdose is reported as a non-serious Event of Clinical Interest (ECI), using the terminology “accidental or intentional overdose without adverse effect.”

All reports of overdose with and without an adverse event must be reported within 24 hours to the Sponsor and within 2 working days hours to Merck Global Safety. (Attn: Worldwide Product Safety; [REDACTED]).

10.52 Reporting of Pregnancy and Lactation to the Sponsor and to Merck

Although pregnancy and lactation are not considered adverse events, it is the responsibility of investigators or their designees to report any pregnancy or lactation in a subject (spontaneously reported to them), including the pregnancy of a male subject's female partner that occurs during the trial or within 120 days of completing the trial, or 30 days following cessation of treatment if the subject initiates new anticancer therapy, whichever is earlier. All subjects and female partners of male subjects who become pregnant must be followed to the completion/termination of the pregnancy. Pregnancy outcomes of spontaneous abortion, missed abortion, benign hydatidiform mole, blighted ovum, fetal death, intrauterine death, miscarriage and stillbirth must be reported as serious events (Important Medical Events). If the pregnancy continues to term, the outcome (health of infant) must also be reported.

Such events must be reported within 24 hours to the Sponsor and within 2 working days to Merck Global Safety. (Attn: Worldwide Product Safety; [REDACTED]).

10.53 Immediate Reporting of Adverse Events to Merck

Serious Adverse Events

A serious adverse event is any adverse event occurring at any dose or during any use of Merck's product that:

- Results in death;
- Is life threatening;
- Results in persistent or significant disability/incapacity;
- Results in or prolongs an existing inpatient hospitalization;
- Is a congenital anomaly/birth defect;
- Is a new cancer (that is not a condition of the study);
- Is associated with an overdose;
- Is another important medical event

Any serious adverse event, or follow up to a serious adverse event, including death due to any cause other than progression of the cancer under study that occurs to any subject from the time the consent is signed through 90 days following cessation of treatment, or the initiation of new anti-cancer therapy, whichever is earlier, whether or not related to Merck product, must be reported within 24 hours to the Sponsor and within 2 working days to Merck Global Safety.

Non-serious Events of Clinical Interest will be forwarded to Merck Global Safety and will be handled in the same manner as SAEs.

Additionally, any serious adverse event, considered by an investigator who is a qualified physician to be related to Merck product that is brought to the attention of the investigator at any time outside of the time period specified in the previous paragraph also must be reported immediately to the Sponsor and to Merck.

10.54 SAE reports and any other relevant safety information are to be forwarded to the Merck Global Safety facsimile number: [REDACTED]

A copy of all 15 Day Reports and Annual Progress Reports is submitted as required by FDA, or other local regulators. Investigators will cross reference this submission according to local regulations to the Merck Investigational Compound Number (IND, CSA, etc.) at the time of submission. Additionally investigators will submit a copy of these reports to Merck & Co., Inc. (Attn: Worldwide Product Safety; [REDACTED]) at the time of submission to FDA.

All subjects with serious adverse events must be followed up for outcome.

10.55 Events of Clinical Interest

Selected non-serious and serious adverse events are also known as Events of Clinical Interest (ECI) and must be recorded as such on the Adverse Event case report forms/worksheets and reported within 24 hours to the Sponsor and within 2 working days to Merck Global Safety. (Attn: Worldwide Product Safety; [REDACTED])

Events of clinical interest for this trial include:

1. An overdose of Merck product, as defined above - Definition of an Overdose for This Protocol and Reporting of Overdose to the Sponsor, that is not associated with clinical symptoms or abnormal laboratory results.
2. An elevated AST or ALT lab value that is greater than or equal to 3X the upper limit of normal and an elevated total bilirubin lab value that is greater than or equal to 2X the upper limit of normal and, at the same time, an alkaline

phosphatase lab value that is less than 2X the upper limit of normal, as determined by way of protocol-specified laboratory testing or unscheduled laboratory testing.*

*Note: These criteria are based upon available regulatory guidance documents. The purpose of the criteria is to specify a threshold of abnormal hepatic tests that may require an additional evaluation for an underlying etiology. The trial site guidance for assessment and follow up of these criteria can be found in the Investigator Trial File Binder (or equivalent).

10.56 Additional adverse events:

A separate guidance document has been provided entitled “Event of Clinical Interest Guidance Document” (previously entitled, “Event of Clinical Interest and Immune-Related Adverse Event Guidance Document”). This document can be found in Appendix 4 and provides guidance regarding identification, evaluation and management of ECIs and irAEs.

ECIs (both non-serious and serious adverse events) identified in this guidance document from the date of first dose through 90 days following cessation of treatment, or 30 days after the initiation of a new anticancer therapy, whichever is earlier, need to be reported within 24 hours to the Sponsor and within 2 working days to Merck Global Safety. (Attn: Worldwide Product Safety; [REDACTED]), regardless of attribution to study treatment, consistent with standard SAE reporting guidelines.

Subjects should be assessed for possible ECIs prior to each dose. Lab results should be evaluated and subjects should be asked for signs and symptoms suggestive of an immune-related event. Subjects who develop an ECI thought to be immune-related should have additional testing to rule out other etiologic causes. If lab results or symptoms indicate a possible immune-related ECI, then additional testing should be performed to rule out other etiologic causes. If no other cause is found, then it is assumed to be immune-related.

10.6 Special Situations for Expedited Reporting

Exceptions to Expedited Reporting: EXPECTED Serious Adverse Events¹

An expedited report may not be required for specific Grade 1, 2, 3 and 4 Serious Adverse Events. Any protocol specific reporting procedures **MUST BE SPECIFIED BELOW** and will **supersede** the standard Expedited Adverse Event Reporting Requirements (see footnote 1):

CTCAE System/Organ/Class (SOC)	Adverse event/Symptoms	CTCAE Grade at which the event will not be expeditedly reported
General disorders and administrations site conditions	Fatigue	≤Grade 3
Gastrointestinal	Vomiting	≤Grade 3
	Nausea	≤Grade 3
	Diarrhea	≤Grade 3
Investigations	Neutrophil count decreased	≤Grade 4
	White blood cell count decreased	≤Grade 4

CTCAE System/Organ/Class (SOC)	Adverse event/Symptoms	CTCAE Grade at which the event will not be expeditedly reported
	Lymphocyte count decreased	≤Grade 4
	Platelet count decreased	≤Grade 4
Blood and lymphatic system disorders	Anemia	≤Grade 4

¹ These exceptions only apply if the adverse event does not result in hospitalization. If the adverse event results in hospitalization, then the standard expedited adverse events reporting requirements must be followed.

Specific protocol exceptions to expedited reporting should be reported expeditiously by investigators **ONLY** if they exceed the expected grade of the event.

10.7 Other Required Reporting

10.71 Persistent or Significant Disabilities/Incapacities

Any AE that results in persistent or significant incapacity or substantial disruption of the ability to conduct normal life functions (formerly referred to as disabilities), congenital abnormalities or birth defects, must be reported immediately if they occur at any time following treatment with an agent under an IND/IDE since they are considered to be a serious AE and must be reported to the sponsor as specified in 21 CFR 312.64(b).

10.72 Death

Any death occurring within 30 days of the last dose, regardless of attribution to an agent/intervention under an IND/IDE requires expedited reporting within 24-hours.

Any death occurring greater than 30 days with an attribution of possible, probable, or definite to an agent/intervention under an IND/IDE requires expedited reporting within 24-hours.

Reportable categories of Death

- Death attributable to a CTCAE term.
- Death Neonatal: A disorder characterized by cessation of life during the first 28 days of life. Death NOS: A cessation of life that cannot be attributed to a CTCAE term associated with Grade 5.
- Sudden death NOS: A sudden (defined as instant or within one hour of the onset of symptoms) or an unobserved cessation of life that cannot be attributed to a CTCAE term associated with Grade 5.
- Death due to progressive disease should be reported as **Grade 5 “Neoplasms benign, malignant and unspecified (incl cysts and polyps) – Other (Progressive Disease)”** under the system organ class (SOC) of the same name. Evidence that the death was a manifestation of underlying disease (e.g., radiological changes suggesting tumor growth or progression: clinical deterioration associated with a disease process) should be submitted.

- Any death occurring **within 30 days** of the last dose, regardless of attribution to the investigational agent/intervention requires expedited reporting within 24 hours.
- Any death occurring greater than 30 days after the last does of the investigational agent/intervention requires expedited reporting within 24 hours only if it is possibly, probably, or definitely related to the investigational agent/intervention.

10.73 Secondary Malignancy

- A *secondary malignancy* is a cancer caused by treatment for a previous malignancy (e.g., treatment with investigational agent/intervention, radiation or chemotherapy). A secondary malignancy is not considered a metastasis of the initial neoplasm.
- All secondary malignancies that occur following treatment with an agent under an IND/IDE be reported. Three options are available to describe the event:
 - Leukemia secondary to oncology chemotherapy (e.g., Acute Myelocytic Leukemia [AML])
 - Myelodysplastic syndrome (MDS)
 - Treatment-related secondary malignancy
- Any malignancy possibly related to cancer treatment (including AML/MDS) should also be reported via the routine reporting mechanisms outlined in each protocol.

10.74 Second Malignancy

A second malignancy is one unrelated to the treatment of a prior malignancy (and is NOT a metastasis from the initial malignancy). Second malignancies require ONLY routine reporting.

10.75 Procedures for Reporting Drug Exposure During Pregnancy and Birth Events

If a woman becomes pregnant or suspects that she is pregnant while participating in this study, she must inform the investigator immediately and permanently discontinue study drug.

Suggested Pregnancy Reporting Form:

- Pregnancy Report Form

Use form available from the CTEP protocol development page:

http://ctep.cancer.gov/protocolDevelopment/electronic_applications/docs/PregnancyReportFormUpdated.pdf

Mayo Clinic Cancer Center (MCCC) Institutions: Provide copies, along with the UPIRTSO cover sheet, by email to the MCCC Regulatory Affairs Unit (RAU) Risk Information Specialist at [REDACTED], who will determine and complete IRB reporting. The RAU will submit to the MCCC SAE Coordinator and the MCCC IND Coordinator to determine if FDA submission is needed.

Non Mayo Clinic institutions: Submit forms via email to Mayo Clinic Cancer Center CRO [REDACTED]. The CRO will submit to the MCCC SAE Coordinator and to the MCCC IND Coordinator.

10.8 Required Routine Reporting

Adverse events to be graded at each evaluation and pretreatment symptoms/conditions to be evaluated at baseline per the CTCAE v4.0 grading unless otherwise stated in the table below:

SYSTEM ORGAN CLASS	Adverse event/Symptoms	Baseline	Each evaluation
Investigations	Creatinine increased	X	X
	Neutrophil count decreased	X	X
	Platelet count decreased	X	X
	White Blood cell decreased (WBC)	X	X
General disorders and administration site conditions	Fatigue	X	X
Gastrointestinal Disorders	Nausea	X	X
	Vomiting	X	X
	Baseline # of Stools	X	
	Diarrhea		X
	Constipation		X
Infections and infestations	Sepsis	X	X
Blood and lymphatic system disorders	Anemia	X	X
	Febrile neutropenia	X	X
Skin and subcutaneous tissue disorders	Rash, maculopapular	X	X

- 10.81 Submit via appropriate MCCC Case Report Forms (i.e., paper or electronic, as applicable) the following AEs experienced by a patient and not specified in Section 10.5:
- 10.811 Grade 2 AEs deemed *possibly, probably, or definitely* related to the study treatment or procedure.
 - 10.812 Grade 3 and 4 AEs regardless of attribution to the study treatment or procedure.
 - 10.813 Grade 5 AEs (Deaths)
 - 10.8131 Any death within 30 days of the patient's last study treatment or procedure regardless of attribution to the study treatment or procedure.
 - 10.8132 Any death more than 30 days after the patient's last study treatment or procedure that is felt to be at least possibly treatment related must also be submitted as a Grade 5 AE, with a CTCAE type and attribution assigned.
- 10.83 Refer to the instructions in the Forms Packet (or electronic data entry screens, as applicable) regarding the submission of late occurring AEs following completion of the Active Monitoring Phase (i.e., compliance with Test Schedule in Section 4.0).

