2.2 Secondary

2.21. To determine the \geq partial response (PR) rate after 4 cycles of treatment with Pembrolizumab added to standard doses of lenalidomide and dexamethasone.

2.22 To determine the \geq VGPR response rate at any time during treatment with Pembrolizumab added to standard doses of lenalidomide and dexamethasone.

2.23 To determine the progression free survival and overall survival among patients with previously untreated symptomatic MM following treatment with the combination of pembrolizumab, lenalidomide and dexamethasone.

2.24 To determine the toxicities associated with pembrolizumab added to standard doses of lenalidomide and dexamethasone in patients with previously untreated symptomatic MM.

2.25 To determine the success rate of stem cell collection following initial therapy with the combination of pembrolizumab, lenalidomide and dexamethasone in patients with newly diagnosed MM.

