4.0 Test Schedule

4.1 Schedule of assessments

Tests and Procedures	Screening		Active Treatment ¹						
	≤30 days	≤14 days	Cycles 1-3 to be repeated beyond 3 cycles						
			Cycle 1		Cycle 2		Cycle 3		End of Induction treatment
			Weekly (For first 2 cycles)	Cycle 1, Day 1, Pre-treatment ¹⁰	Pembrolizumab infusion Cycle 1, Day 22, Pre-treatment ¹¹	Cycle 2, Day 1, Pre-treatment	Pembrolizumab infusion Cycle 2, Day 15, Pre-treatment ¹¹	Cycle 3, Day 1, Pre-treatment	
Complete medical history	X								
Adverse Event monitoring		X		X		X		X	X
Physical exam, including weight, vital signs		X		X		X		X	X
Height		X							
Performance status (ECOG scale)		X		X		X		X	X
CBC with diff (includes hemoglobin, ANC, WBC with complete differential, platelets)		X	X	X	X	X	X	X	X
Prothrombin time (PT)	X								
Chemistry group to include sodium, potassium, glucose, alkaline phosphatase; Total and Direct bilirubin; SGOT (AST); SGPT (ALT); serum creatinine, calcium		X	X	X	X	X	X	X	X
LDH, Beta ₂ -microglobulin, Plasma cell assessment	X								
sTSH	X			Every 6 months while on treatment					
Electrophoresis of serum and urine (SPEP/UPEP)		X		X ⁹		X ⁹		X ⁹	X ⁹
Affected Immunoglobulin ²		X		X		X		X	X
Immunofixation serum and urine	X			X ³		X ³		X ³	X ³
Immunoglobulin free light chain		X		X ⁴		X ⁴		X ⁴	X ⁴
X-ray skeletal survey or low dose whole body CT	X								
Bone marrow aspirate and biopsy, myeloma FISH, plasma cell proliferation, and flow cytometry	X			X ⁵		X ⁵		X ⁵	X ⁵

	Screening		Active Treatment ¹							
	≤30 days	≤14 days	Cycles 1-3 to be repeated beyond 3 cycles							
			Cycle 1		Cycle 2		Cycle 3		End of Induction treatment	
			Weekly (For first 2 cycles)	Cycle 1, Day 1, Pre-treatment ¹⁰	Pembrolizumab infusion Cycle 1, Day 22, Pre-treatment ¹¹	Cycle 2, Day 1, Pre-treatment	Pembrolizumab infusion Cycle 2, Day 15, Pre-treatment ¹¹	Cycle 3, Day 1, Pre-treatment		Pembrolizumab infusion Cycle 3, Day 8, Pre-treatment ¹¹
Tests and Procedures										
Research bone marrow ^R (IRB 521-93)	X			X ⁵		X ⁵		X ⁵		X ⁵
Research blood sample ^R (IRB 521-93)	X			X ⁶		X ⁶		X ⁶		
Chest x-ray	X									
Serum pregnancy test		X ⁷								
Patient Medication Diary (Appendix II) ⁸ .				X		X		X		X

Cycle length during induction = 28 days

- 1) All scheduled visits will have a window of ± 4 days, except pembrolizumab infusion days which will have a window of ± 1 day

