16.32 Secondary Outcome Analyses

- 16.321 The \geq PR response rate after 4 cycles of induction treatment with pembrolizumab added to lenalidomide and dexamethasone will be estimated by the number of patients who achieve a PR, VGPR, CR, or sCR after 4 cycles divided by the total number of evaluable patients. Exact binomial 95% confidence intervals for the true success rate will be calculated.
- 16.322 The \geq VGPR response rate at any time during treatment with pembrolizumab added to lenalidomide and dexamethasone will be estimated by the number of patients who achieve a VGPR, CR, or sCR at any time divided by the total number of evaluable patients. Exact binomial 95% confidence intervals for the true success rate will be calculated.
- 16.323 Survival time is defined as the time from registration to death due to any cause. The distribution of survival time will be estimated using the method of Kaplan-Meier⁷.
- 16.324 Progression-free survival is defined as the time from registration to the earliest date of documentation of disease progression or death due to any cause. Patients who receive subsequent treatment for myeloma before disease progression will be censored on the date of their last disease assessment prior to initiation of the subsequent treatment. Transplant will not be considered subsequent treatment. The distribution of progression-free survival will be estimated using the method of Kaplan-Meier
- 16.325 Adverse Events: All eligible patients that have initiated treatment will be considered evaluable for assessing adverse event rate(s). The maximum grade for each type of adverse event will be recorded for each patient, and frequency tables will be reviewed to determine patterns. Additionally, the relationship of the adverse event(s) to the study treatment will be taken into consideration.
- 16.326 The success rate of stem cell collection following initial therapy with the combination of pembrolizumab, lenalidomide and dexamethasone in patients with newly diagnosed MM will be estimated by the number of patients with a successful stem cell collection divided by the total number of evaluable patients. Exact binomial 95% confidence intervals for the true success rate will be calculated.

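### Sections 10.5 and 10.81 conflict on which adverse events reach the case report form, so low-grade rates for most named pembrolizumab toxicities may be incomplete or depend on attribution

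*Combined protocol and SAP*

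**What the plan says.** Goal 2.24 is "To determine the toxicities associated with pembrolizumab added to standard doses of lenalidomide and dexamethasone" in this population. Section 16.325 serves it with a single analysis: "The maximum grade for each type of adverse event will be recorded for each patient", followed by frequency tables. It does not say which captured events feed those tables.

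Two sections govern what is captured.

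- Section 10.5, headed as Merck's requirements: "All adverse events will be recorded from the time the consent form is signed through 30 days following cessation of treatment", on the adverse event case report forms or worksheets. There is no limit by grade or attribution.
- Section 10.8 opens with a table of terms: "Adverse events to be graded at each evaluation and pretreatment symptoms/conditions to be evaluated at baseline per the CTCAE v4.0 grading". Section 10.81 then asks for submission, on the cancer center's forms, of "the following AEs experienced by a patient and not specified in Section 10.5". The list that follows is "Grade 2 AEs deemed *possibly, probably, or definitely* related to the study treatment or procedure" (10.811), "Grade 3 and 4 AEs regardless of attribution to the study treatment or procedure" (10.812), and deaths within 30 days of the last treatment or later if at least possibly related (10.813).

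Two other routes bring events onto the forms. Section 10.55 requires events of clinical interest (ECIs), serious or not, to be entered on the adverse event form. Section 10.56 calls for ECI assessment before each dose, with review of laboratory results and questions about immune-related symptoms. Section 10.11 sends events reported by expedited mechanisms through routine data reporting as well.

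**The concern.** The two rules cannot both define the adverse event dataset. Under 10.5 a Grade 1 rise in a liver enzyme is on the form; under 10.81 it need not be. A Grade 2 event is on the form under 10.5 whatever its cause, but under 10.81 only if the investigator calls it at least possibly related. In an open single-arm trial, that judgement would then decide whether some Grade 2 events enter the tables at all.

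The terms protected from this are those in the 10.8 table, and that table has few of the immune-type events for which the protocol manages pembrolizumab. What is at stake is whether the low-grade columns of the 16.325 tables mean the same thing for every event type and every patient.

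**Working it through.** The plan states no figure on this point to reproduce. The check compares texts and makes one count.

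**Step 1. Read 10.81 literally.** It excludes what 10.5 specifies. Section 10.5 specifies all adverse events. All minus all leaves nothing, so 10.81 has no content and 10.5 alone governs. On that reading nothing is lost.

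**Step 2. Find the intended target.** Cross-references elsewhere in Section 10 are also out of step. Section 10.11 cites 10.5 for attribution, which is in 10.3. Sections 10.11 and 10.31 cite 10.6 for routine reporting, but 10.6 lists exceptions to expedited reporting. Section 6.19 cites 10.8 correctly for baseline symptoms. The pointer in 10.81 makes sense only if it means the table in 10.8.

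**Step 3. Compare the rules for an event not in the 10.8 table.**

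| Event | 10.5 | 10.81 as intended |
|---|---|---|
| Grade 1, not an ECI and not serious | on form | not submitted |
| Grade 2, unlikely related or unrelated, not an ECI and not serious | on form | not submitted |
| Grade 2, at least possibly related | on form | submitted |
| Grade 3 or 4, any cause | on form | submitted |
| ECI or serious event | on form | on form through 10.55 or 10.11 |

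Only the first two rows differ. In 10.811, related means related to study treatment or procedure, so a Grade 2 event put down to lenalidomide or dexamethasone is still submitted.

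**Step 4. Count the named pembrolizumab rows.** The Section 8.2 table names nine, apart from the catch-all for other drug-related events.

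| Section 8.2 row | In the 10.8 table? |
|---|---|
| Diarrhea or colitis | in part (diarrhea) |
| AST, ALT or bilirubin | no |
| Type 1 diabetes or hyperglycemia | no |
| Hypophysitis | no |
| Hyperthyroidism | no |
| Hypothyroidism | no |
| Infusion related reaction | no |
| Pneumonitis | no |
| Acute kidney injury or chronic kidney disease | in part (creatinine) |

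Two are covered at least in part; 9 - 2 = 7 are not.

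**Step 5. Scale.** With the maximum of 41 patients (16.12: 37 + 4), each patient missing from a row moves its any-grade frequency by 1/41 = 2.4 percentage points.

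- Section 15.17 puts hypothyroidism, hyperthyroidism, infusion reactions and pneumonitis at 1% to 10% with pembrolizumab: 41 x 0.01 = 0.41 to 41 x 0.10 = 4.1 patients each.
- It puts hepatitis, hypophysitis and type 1 diabetes below 1%: fewer than 0.41 patients each.
- Section 15.27 lists abnormal liver function tests and hyperglycemia at 10% or more with lenalidomide: 4.1 patients or more each.

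These figures assume the listed frequencies carry over to this combination. They are not split by grade, so the share falling in the first two rows of Step 3 cannot be calculated.

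**Step 6. Stopping rule.** Section 16.42 counts Grade 4 or higher non-hematologic events at least possibly related to treatment. Sections 10.812 and 10.813 capture these, as does 10.5, so the rule is unaffected.

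**The case against.** The strongest reply is that this is mainly editorial. Section 10.5 describes recording for the drug supplier, on forms or worksheets; 10.81 describes submission to the cancer center. Recording and submission can differ without contradiction. That is fair as far as it goes, but 16.325 does not say which of the two it tabulates, so the question remains open where it matters.

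The second reply is that ECI assessment already covers immune events. This narrows the gap considerably. It does not demonstrably close it: the only ECIs named in 10.55 are an overdose without symptoms and a combined transaminase, bilirubin and alkaline phosphatase threshold, which an isolated ALT rise does not meet. The remainder are in a guidance document that is not in the text reviewed. Its absence is not a fault of the plan, but its coverage cannot be assumed in either direction.

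Third, a dose-modification table is not a standard for a solicited list. Agreed: 7 of 9 counts terms missing from the 10.8 table, not lost data.

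Three stronger readings are tempting, and the documents do not support them.

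- A reader might infer that immune toxicities are unsolicited and that their rates will be incomplete. Section 10.56 has patients questioned and laboratory results reviewed before each dose, and under 10.5 every event is captured.
- A reader might infer that lenalidomide toxicity is fully captured and pembrolizumab toxicity is not. Section 15.1 lists rash, diarrhea and fatigue as common with pembrolizumab, and all three are in the 10.8 table.
- A reader might infer a gap in thyroid data from the sTSH row in 4.1, which after screening reads "Every 6 months while on treatment". Section 16.325 sets no four-cycle toxicity period; four cycles is the response window. Section 9.9c provides for periodic and clinically prompted thyroid monitoring. No change to sTSH timing is claimed.

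**Conclusion.** The concern holds in a limited form. Sections 10.5 and 10.81 conflict, and the cross-reference in 10.81 is unworkable as written. If sites follow 10.81 with the 10.8 table as its target, Grade 1 events and Grade 2 events judged unlikely related or unrelated may be missing when they are outside that table and are neither ECIs nor serious. Seven of the nine named pembrolizumab rows are exposed to this.

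The effect is confined to the low-grade part of the 16.325 tables for goal 2.24. Related Grade 2 and all Grade 3 and 4 frequencies, serious events, ECIs, the stopping rule and the primary endpoint are untouched.

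The conclusion assumes that terms in the 10.8 table are submitted at every grade, that the ECI guidance does not already sweep in all low-grade immune events, and that the case report form packet, which was not available, contains no overriding rule. It is a change that should be made, not one on which the trial's validity depends.

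**What to change.** 1. In 10.81, replace the reference to Section 10.5 with: *not listed in the table in Section 10.8*.
2. State one case report form capture rule, by grade and attribution, and have 10.5, 10.8 and 16.325 all refer to it. If recording for the drug supplier is meant to be broader than submission to the cancer center, say so, and say which dataset 16.325 tabulates.
3. Add nine terms to the each-evaluation list in 10.8, recorded at all grades regardless of attribution: ALT increased, AST increased, bilirubin increased, hyperglycemia, hypothyroidism, hyperthyroidism, hypophysitis, pneumonitis and infusion-related reaction.

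The cost is protocol wording, about nine extra form lines and slightly more data entry. Liver chemistry and glucose are already drawn under 4.1, and no new test or visit is needed.
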